4.2.3 Second 6-Week Arm

Following the one-week washout period, patients will start the second arm therapy for the next six weeks of nightly use. The procedure will be exactly the same as for the first arm, described above except that the device pressure range will be retained at the same settings that were present during the bulk of the first arm.

4.2.4 TPAP Arm Specifics

The TPAP arm involves other pressure settings because the therapy involves reducing pressure in two steps starting at inhalation and following through the peak of exhalation. An auto-adjusting algorithm will continuously choose the pressure within the active pressure range, and the settings for the two pressure drops will also instantly and continuously adjust to those specified in Table 1 above.

4.2.5 Risk-Benefit Analysis

All patients will be using a Sefam S.Box as their therapy device. Although the S.Box does not have 510K approval, it is CE-marked and approved for use in Europe. All TheraPAP algorithms will be thoroughly verified and validated for safety and efficacy in each device according to the SleepRes QMS before being provided to a patient. When not in use and when returned, these devices will be sequestered in a locked location. TheraPAP is a new OSA therapy designed to improve CPAP comfort. Testing in awake PAP-naïve patients thus far has shown a preference of it over CPAP. Thus, we expect there are no risks associated with it.

Regarding benefits to the participants:

- It is anticipated that patients on the TheraPAP arm of the study will find it more comfortable than regular CPAP and hopefully sleep better.

- The results of the study could yield future benefit to the participants in terms of wider treatment alternatives for their OSA.

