1.1 Synopsis

Protocol Title: A Prospective, Randomized, Crossover Study of the TheraPAP Compared to Automatic Adjusting Positive Airway Pressure (APAP) for the Treatment of Obstructive Sleep Apnea (OSA)

Protocol Name/Number: TheraPAP Adherence 1

Sponsor: SleepRes, PLLC

Rationale: TheraPAP is a prototype device (with full documented electrical and isolation safety) being developed by SleepRes for the treatment of obstructive sleep apnea (OSA) that can deliver either standard CPAP at a set pressure or what is called TPAP¹. TPAP is a pressure control algorithm that lowers the pressure from the set pressure at the beginning of inspiration and does not return the pressure to the full set level until about halfway through expiration. The present study, TheraPAP Adherence 1, is a randomized crossover study designed to examine the difference in therapy adherence between TPAP vs. CPAP alone in the treatment of OSA.

Overall Design:

The TheraPAP Adherence Study is a randomized, crossover study in treatment naive participants with OSA in which the adherence to therapy will be compared between TPAP and standard APAP. Because all participants will breathe on both therapy types and those therapy types are individually unique in feel, blinding is not possible. Participants will be chosen from a pool of patients who are PAP-naïve and who have received either a PSG (in-lab polysomnogram), split-night study (in-lab PSG and pressure titration) or home sleep study (HST) within the previous 3 months.

Upon signing an informed consent, participants will be randomly assigned to start on either the TPAP or APAP arms when they arrive at the office to pick up their Sefam S.Box with TheraPAP algorithms integrated. Each participant will then be given their new equipment and will be trained in proper use for both arms of the study so that they will not need to appear at the office again until the study is completed. In both the APAP and TPAP arms, participants will have their therapy set to 5-20 cmH₂O for three nights. The pressure range will then be narrowed to ± 2 cmH₂O around their 95% pressure level as assessed during the third night. This same pressure range will be used during the second arm for each patient.

¹ TPAP will be used herein to refer to the active treatment.

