4.1 Overall Design

Safety issues regarding this study are detailed in Appendix 1: Regulatory, Ethical, and Study Oversight Considerations.

The TheraPAP Adherence 1 Study is a randomized, controlled, crossover study in PAP-naïve participants with OSA. Pre-screening is conducted to establish potential eligibility based on an in-lab polysomnogram (PSG), a PSG split-night PSG/titration or a home sleep study (HST) that has been conducted within the previous 3 months. Participants would then be recruited as described below. For those who consent, they will be given the equipment and instructions to complete both arms of the study but will have their therapy device set to the parameters necessary to start the first arm, which will be randomly assigned. They will use the device nightly for 6 weeks, after which they will use no therapy for 1 full week (washout period). During this washout period, their therapy device will be remotely set to their second arm. When they restart therapy, they will use the device nightly for a further 6 weeks. During each arm, various data will be remotely collected from their therapy device, and after completion of each arm, they will fill out 3 questionnaires and average data during the 6 weeks of that arm will be downloaded. Once all activities are completed, they will be eligible to receive the incentive pay and their involvement will be completed.

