4.2 Detailed Design

4.2.1 Pre-Screening

The first phase of recruiting for the TheraPAP Adherence 1 study will be done during the phone follow up during which the patients will be scheduled to come to the office of Sleep Centers of Middle Tennessee (SCMT) to collect their CPAP equipment. The following regarding the study will be conveyed to them: goals, a summary protocol, risks/benefits, other activities required by them, financial compensation and timing. They will also be asked for verbal permission to review their records so that office personnel can conduct a preliminary screening for eligibility. If they agree and show interest based on the first phase, they will be added to the eligibility roster.

The second phase of recruiting will be conducted when they come into the office to pick up the equipment. The coordinator will review the material related to the study, as well as the details within the informed consent. If the patient agrees to continue, they will sign the informed

consent in ink and be enrolled in the study. The coordinator will conduct a final check that the patient satisfies all enrollment criteria. After this, they will be enrolled in the study.

They will then be randomly assigned to start in either the APAP or TPAP arms of the study, and their equipment will be set up by the coordinating staff to operate according to the randomly chosen arm. During this setup, the pressure range will also be set to 5-20 cmH₂O irrespective of study arm. They will receive this equipment for the study, then be given instructions for use on both arms both verbally and through material that they can take home.

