4.2.2 First 6-Week Arm

Patients will start using their equipment the first night. The study coordinator will monitor usage nightly and after the third night with a minimum of 5 hours of use, they will remotely adjust the device pressure range to P95 ± 2 cmH₂O, using the P95 from the third night. This range will be used for the remainder of both arms of the study. During the study, daily remote collection of usage will be conducted both for later primary endpoint analysis and to guide further contact with the patient if they need help.

During usage in the first arm, P95 and AHI will be monitored to assure that the patient is receiving proper therapy. If P95 is near the upper limit and the AHI is above 5 events per hour, the range will be bumped up by 2 cmH₂O.

A contact schedule will also be set up with each patient to follow up on any needs for help. Similar interaction is customary with new CPAP patients. The schedule is as follows and will be conducted on both arms of the study:

- 1 Day Phone Call (+2 days)
- 7 Day Phone Call (+/- 3 days)
- 14 Day Phone Call (+/- 3 days) IF deemed necessary per 7 Day compliance
- 28 Day Phone Call (+/- 3 days)

Participants using the device less than an average of 5 hours per night during the first week will be contacted on a more regular basis (weekly until 5 hour per night use is achieved) to address any problems and encourage use. If patients discontinue use of the device during the home use period, they will still be encouraged to complete surveys per protocol. If a patient refuses to complete such surveys, they will be considered lost to follow up and excluded from efficacy analysis.

At the end of the 6-week period, patients will stop using any sleep therapy for 1 week as a washout between arms. The study coordinator will remotely switch the mode of operation of the

therapy device to that for the second arm employing the same pressure range as was used in the bulk of the first arm. Patients will be asked to fill out the questionnaires during this period (ESS and FOSQ). Additionally, the following data averaged over the 6-week period of the trial will be downloaded from the device:

- Usage
- Leak
- P95
- AHI

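### Section 4.2.5 states a benefit for TPAP only and expects no risk; if the recruitment message follows it, an unblinded usage comparison could tilt towards TPAP

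*Protocol*

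**What the plan says.** Section 4.2.5 lists two benefits to participants. The first concerns one therapy: "It is anticipated that patients on the TheraPAP arm of the study will find it more comfortable than regular CPAP and hopefully sleep better". The second comes from the research and not from either mode: "The results of the study could yield future benefit to the participants in terms of wider treatment alternatives for their OSA". No benefit is stated for APAP.

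On risk, the section reports that "Testing in awake PAP-naïve patients thus far has shown a preference of it over CPAP" and concludes in the next sentence: "Thus, we expect there are no risks associated with it". Earlier in the paragraph it says that the algorithms will be verified and validated on each device under the sponsor's quality system. Section 6.1 adds that they have been tested in the sponsor's laboratory.

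Section 4.2.1 describes the first recruitment contact, by phone and before consent: "The following regarding the study will be conveyed to them: goals, a summary protocol, risks/benefits".

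The Synopsis says of the two modes that "those therapy types are individually unique in feel, blinding is not possible". Section 4.1 describes a "randomized, controlled, crossover study in PAP-naïve participants with OSA". The primary endpoint in Section 3 is nightly usage; ESS, FOSQ and AHI are among the secondary endpoints. Section 5.5, on minimizing bias, offers only the random choice of starting arm.

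**The concern.** The trial asks whether people use TPAP more than APAP. The device records usage, but the participant decides it each night. ESS and FOSQ are self-reported. A PAP-naïve person who hears beforehand that one mode should feel better has no experience of PAP to set against that message, and will know which mode is running. Random order balances period effects. It does not balance an expectation that attaches to TPAP in whichever period TPAP is used. A positive result could then partly reflect what participants were led to expect.

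The risk statement is a second weakness in the same text. Preference while awake is evidence about comfort. It does not bear on airway obstruction during sleep at a lower inspiratory pressure, which is the risk that the mechanism raises.

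**Working it through.** **Inputs from Section 7.1.** 14 completers per sequence (28 in all), a minimum difference of 0.5 h, an SD of paired differences of 1 h, one-sided 5%. The test is taken to be in TPAP's favour, because Section 2.1 asks whether TPAP improves adherence. Section 7.1 also gives 1 h as the within-subject SD. Read that way, the SD of a difference is √2 × 1 = 1.41 h, so both values are carried.

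**The plan's own figure.** Noncentrality = 0.5 × √28 / 1 = 2.646. With 26 degrees of freedom the one-sided 5% critical value is 1.706, and the noncentral t gives 82.4% power. The stated figure of about 82% reproduces.

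**Smallest significant observed difference.** Critical value × SD / √28:
- SD 1 h: 1.706 × 1 / 5.292 = 0.322 h, about 19 minutes a night.
- SD 1.41 h: 1.706 × 1.414 / 5.292 = 0.456 h, about 27 minutes a night.

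**Effect of an expectation shift.** Suppose that TPAP has no true effect and that expectation moves mean usage by b hours towards TPAP. The chance of a significant result is P(T > 1.706), where T is noncentral t with 26 degrees of freedom and noncentrality b√28/SD. The documents give no value for b, so the range is assumed.

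| Assumed shift b | False-positive rate, SD 1 h | False-positive rate, SD 1.41 h |
|---|---|---|
| 0 h | 5.0% | 5.0% |
| 0.1 h | 12.9% | 10.0% |
| 0.2 h | 27.0% | 18.0% |
| 0.3 h | 46.1% | 29.1% |

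**The risk statement against the rest of the protocol.**
- The evidence of similar residual AHI in Section 2.2.3 comes from a fixed resistor in the inspiratory line. That section presents TPAP as different because its pressure drop is adjustable.
- The verification and laboratory-testing statements in 4.2.5 and 6.1 are general. Neither reports residual AHI in sleeping patients on this algorithm.
- Section 3 makes AHI a secondary endpoint, so the trial itself sets out to evaluate it.
- Every participant spends one week without therapy between arms (Sections 4.1 and 4.2.2). The risk discussion in 4.2.5 does not mention this.

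**The case against.** The strongest objection is that the link from 4.2.5 to participants is inferred. Section 4.2.1 says that risks and benefits are conveyed, not that this text is read out. Neither the script nor the consent form is shown, and the protocol requires an IRB-approved consent that meets 21 CFR 50. This stands. A reader might infer that participants are in fact told TPAP is better, or that they enroll without hearing of possible under-treatment. The documents support neither statement.

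A reader might also take the sentence that "P95 and AHI will be monitored to assure that the patient is receiving proper therapy" as an admission that TPAP may under-treat. It is not one. Section 4.2.2 applies that monitoring in the first arm, whichever mode comes first, after the pressure range has been narrowed. The AHI endpoint is the sounder support.

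Nor does the no-risk conclusion rest on awake preference alone, given the verification and testing statements. And 4.2.5 already discloses that the device lacks 510(k) status, so that is not an omission.

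Three further points are fair. The benefit sentence is hedged. The scheduled calls are the same on both arms. Participants must learn the study's purpose in any case, so some expectation would remain under neutral wording, and nothing in the documents separates the effect of this sentence from novelty or from the open-label design. These points limit how much the fix can achieve. They do not justify a one-sided text.

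**Conclusion.** The point holds as a conditional risk of bias plus a poorly supported risk statement. The protocol's own risk-benefit text favours one arm, its recruitment section directs that risks and benefits be conveyed, and its bias section contains nothing that addresses expectation. If the message follows the text, the bias runs towards TPAP.

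The size cannot be derived from the documents. Over assumed shifts of 0.1 to 0.3 h, the false-positive rate is roughly 13% to 46% (SD 1 h) or 10% to 29% (SD 1.41 h), against a nominal 5%. These figures rest on 28 completers, a one-sided crossover t test with 26 degrees of freedom, no true effect, and a constant shift. They show how sensitive the test is to a shift and do not estimate one.

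On risk, the supportable conclusion is that the protocol cites no evidence on residual apnea during sleep with this algorithm. It does not follow that TPAP under-treats.

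**What to change.** - In 4.2.5, the recruitment script, the consent material and all calls, describe both modes neutrally as treatments for OSA whose relative comfort and use are unknown. Keep the sponsor's hypothesis in Section 2.
- Replace the no-risk conclusion with a statement that residual apnea during sleep at a lower inspiratory pressure is not yet established for this algorithm, and that all participants have one untreated washout week.
- Acknowledge open-label expectation as a limitation, since neutral wording reduces it without removing it.

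The changes should be made before enrolment, because no later analysis can separate expectation from the effect of the algorithm. The cost is rewording and one IRB submission, and recruitment may become slightly less attractive. Sample size, schedule and device settings are untouched.

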4.3 End of Study Definition

Once the second 6-week arm is over and questionnaires have been completed, the patients will return their equipment to the office. Once the equipment is returned, the participants' involvement in the study will be complete and they will be able to receive their study incentive. They will also then be given their regular take-home equipment with usage instructions.

5 Study Population

Eligible participants will be recruited from the pool of PAP-naïve patients who have undergone some form of sleep study and will be receiving CPAP therapy equipment.

5.1 Inclusion Criteria

5.1.1 Age and Sex

1. Between 20 and 70 years of age, inclusive.

5.1.2 OSA Measures

2. Diagnosis of OSA meeting all the following criteria:
 - a. AHI > 10 on a previous PSG or HST (hypopneas requiring 4% desaturation).
 - b. Central apneas < 25% of events
 - c. PLM arousal index < 15

5.1.3 Informed Consent

3. Subject is fluent in English and subject understands the study protocol and is willing and able to comply with study requirements and sign informed consent.
4. Participant voluntarily agrees to participate in this study and signs an Institutional Review Board (IRB)-approved informed consent prior to performing any of the study-related procedures.

5.2 Exclusion Criteria

Participants are excluded from the study if any of the following criteria apply:

5.2.1 Medical Conditions

1. A female of child-bearing potential that is pregnant or intends to become pregnant.
2. Any unstable or severe medical condition of any organ system including congestive heart failure, COPD, renal failure, neuromuscular disease, etc., or at the discretion of the site Principal Investigator (PI).
3. Taking medication that may affect sleep, sleepiness, or alertness including hypnotics, sedatives, alerting agents, stimulants, anticonvulsants, etc.
4. The presence of any other sleep disorder (insomnia, periodic limb movement disorder, etc).

5.2.2 Prior/Concomitant Therapy

5. Prior therapy or treatment for OSA.
6. Chronic oxygen therapy.

5.2.3 Other Exclusions

7. Excessive alcohol consumption (>14 drinks/week).
8. The use of any illegal drug(s).
9. Any condition that in the investigator's opinion would present an unreasonable risk to the participant, or which would interfere with their participation in the study or confound study interpretation.

5.3 Screen Failures

Patients that do not meet the inclusion/exclusion criteria at the outpatient screening visit will not be invited to, or further contacted to, participate in the study.

5.4 Preparation/Handling/Storage/Accountability

Devices will be provided by the sponsor and will be kept in a locked designated area within the DME (Durable Medical Equipment) office. It will only be accessible by office personnel. They will be used only for approved study purposes as designated by the study coordinator who will oversee their use in this study.

5.5 Measures to Minimize Bias

Each participant will begin the study in one of the treatment arms, (either APAP or TPAP). The starting treatment arm is determined by a random number generator, as described in Section 7.2.

5.6 Concomitant Therapy

Usual therapy is allowed as indicated by the patient's general practitioner, except for oxygen therapy, which is an exclusion criterion.

5.7 Discontinuation of Study Treatment

If a clinically significant finding is identified, the Investigator or qualified designee will determine if the participant can continue in the study and if any change in participant management is needed. Any new clinically relevant finding should be reported as an adverse event (AE).

5.8 Stopping Criteria

5.8.1 Individual Participant Stopping Criteria

Participants reporting any SAE considered possibly related or related to study device will be withdrawn from the study.

Any other AE that in the judgment of the Investigator necessitates the participant stopping to protect participant safety, will result in early withdrawal from the study.

5.9 Participant Discontinuation/Withdrawal from the Study

A participant may withdraw from the study at any time at his/her own request or may be withdrawn at any time at the discretion of the Investigator for safety, behavioral, or administrative reasons.

If the participant withdraws consent, the Sponsor may retain and continue to use any data collected before such a withdrawal of consent.

All participants who withdraw from the study with an ongoing AE must be followed until the event is resolved or deemed stable.

Participation may be terminated before completing the study and the reason recorded as follows:

- Withdrawal due to AE
- Participant withdrew consent at their own request, (e.g., intolerance to study procedures)
- At the discretion of the Investigator for safety, behavioral, or administrative reasons
- Other reasons, as they occur

5.10 Participant compensation

Participants will be compensated for their time and participation with an office credit of \$200.

6 Study Assessments and Procedures

Study procedures and their timing are summarized in the SoA.

Adherence to the study design requirements, including those specified in the SoA, is essential and required for study conduct.

All screening evaluations must be completed and reviewed to confirm that potential participants meet all eligibility criteria. The Investigator will maintain a screening log to record details of all participants screened and to confirm eligibility or record reasons for screening failure, as applicable.

6.1 At Home Study

- **Methods:** Equipment taken home for the study (Sefam S.Box and associated patient interface materials) has been given European approval via a CE mark. Additions of TheraPAP algorithms, which have been tested extensively for safety and efficacy in our lab, will be evaluated on the S.Box machines via a testing procedure that is part of our quality system.
- Regular contact with patients according to the call schedule will be conducted and any problems will be discussed and reported.
- Study data reported by the S.Box (usage, P95, leak and AHI) will be averaged over a night and recorded daily through the S.Box remote access system, and will be stored according to HIPAA requirements at the sponsor's office.

6.2 Safety Assessments

Planned time points for all safety assessments are provided in the SoA.

Safety assessments will include measurement of vital signs, monitoring and recording of AEs, SAEs, and recording of study or treatment discontinuations. Effects on OSA and sleep parameters (e.g., sleep time and sleep stages) will also be monitored by PSG.

6.3 Adverse Events and Serious Adverse Events

The definitions of AEs and SAEs can be found in [Appendix 2: Adverse Events: Definitions and Procedures for Recording, Evaluating, Follow-up, and Reporting.](#)

Adverse events will be reported by the participant.

The Investigator and any qualified designees are responsible for detecting, documenting, and reporting events that meet the definition of an AE or SAE and remain responsible for following up on AEs that are serious, considered related to the study device or the study, or that caused the participant to discontinue the study.

